#### **6.1.2 Dosing and Administration**

The Proglucamune® tablets and placebo tablets will be instructed to consume orally 2 tablets/day (containing ~200mg beta glucan) at one sitting, preferably with a meal. The study participants will be administered the study intervention during the course of study (84 days).

Subjects who are currently taking any prescribed medications must agree to maintain their current method and dosing regimen during the course of the study unless recommended otherwise by their physician. In such cases, they will be instructed to take the study treatment (placebo or Proglucamune®) at least 3 hours before or after the prescribed medication. The use of dietary supplements used for the purpose of combating low Qi are prohibited during the study. Chronic use of NSAIDs, laxative, antacids, as well as any lipid lowering medication (prescription, OTC, or herbal), insulin, metformin or other diabetes medication are prohibited in this study. Use of tobacco products including chewing tobacco and all types of cigarettes are prohibited. Any changes in medication schedules or prescription medication for concurrent conditions arising during the course of the study will be reviewed and noted in the case report form (CRF).

### **6.2 Preparation/Handling/Storage/Accountability**

#### **6.2.1 Acquisition and Accountability**

Subjects will be provided with the appropriate treatment tablets (i.e., either placebo or Proglucamune®) and instructed to consume 2 tablets/day at one sitting. Visits scheduled for day 28 (Visit 3) and day 56 (Visit 5) will

collect any unused tablets during the previous 28-day study period as well as distribution of another allotment of tablets (i.e., 60 tablets) sufficient for the forthcoming 28-day study period.

### **6.2.2 Formulation, Appearance, Packaging, and Labeling**

Placebo formula contain excipients (831 mg per tablet) and coating materials. The placebo excipients include microcrystalline cellulose 806mg, Pregelatinized Starch 10.7 mg, croscarmellose sodium 7.11 mg, silicon dioxide: 3.57 mg, and Ascorbyl Palmitate 3.57 mg.

Treatment formula contain active ingredients and excipients (846 mg per tablet) and coating materials.

The treatment active ingredients include Beta-Glucan Complex (Baker's Yeast Extract [Saccharomyces cerevisiae, cell wall]) 125 mg (The w/w yield of prepared extracts in terms of starting crude material: 38%), Reishi Mushroom [Ganoderma lucidum, whole mushroom powder] 125 mg, Shiitaki Mushroom [Lentinula edodes, whole mushroom powder] 25 mg, and Zinc (as Zinc Gluconate) 25mg.

The treatment excipients include Microcrystalline cellulose 426 mg, modified cellulose 90 mg, vegetable fatty acid 10 mg, croscarmellose sodium 5 mg, and silicon dioxide 5 mg, and Hydroxy Propyl Cellulose 9mg.

Treatment and placebo formula contain the same coating materials (Opadry II Complete Film Coating System 57U150022 Red).

### **6.2.3 Product Storage and Stability**

Treatments and placebo tablets should be stored at or below 25°C or 75°F and kept out of reach of children.

### **6.2.4 Preparation**

The study intervention and control product (tablets) can be used directly without any preparation.

## **6.3 Measures to Minimize Bias: Randomization and Blinding**

This study will be a randomized, triple-blind, placebo-controlled, parallel arm design. The participants will be recruited and randomized in a 1:1 ratio to either of two interventions: 1) Daily consumption of the control supplement (placebo), and 2) Daily consumption of the treatment ( $\beta$ -glucan). For randomization, these participants will be first stratified based upon: 1) ethnicity, 2) whether or not the subject has had an influenza vaccine (flu shot) since October 1, 2018, and 3) whether or not the subject currently exhibit a 'cold' as defined by TCM (hereafter referred to as cold\*). These factors will be deemed potential confounders of  $\beta$ -glucan effect. Throughout the trial, including the recruitment and the treatment, all participants and on-site investigators will be blinded to treatment.

Each participant has an emergency envelop, the information of this participant's allocation (treatment group or placebo group) will be include in, and PI will hold onto the envelops. If any participant needs to be unblinded, PI will open the corresponding envelop and notice the relevant physician.

## **6.4 Study Intervention Compliance**

Protocol compliance will be evaluated based on study product returned. That is, compliance will be calculated by determining the number of dosage units taken divided by the number of dosage units expected to have been taken multiplied by 100.

$$\frac{\text{number of dosage units taken}}{\text{number of dosage units expected to have been taken}} \times 100\%$$

Subjects found to have a compliance of <80% or >120% will be censored from the study.

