## **7. Study Intervention Discontinuation and Participant Discontinuation / Withdrawal**

### **7.1 Discontinuation of Study Intervention**

Discontinuation from Proglucamune® or placebo does not mean discontinuation from the study, and remaining study procedures should be completed as indicated by the study protocol. If a clinically significant finding is identified (including, but not limited to changes from baseline) after enrollment, the investigator or qualified designee will determine if any change in participant management is needed. Any new clinically relevant finding (harm) will be reported as an adverse event (AE).

The data to be collected at the time of study intervention discontinuation will include the following: laboratory safety tests, anthropometrics, and vitals.

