#### **7.2.2 Removal by Qualified Investigator**

The Investigator has the discretion to remove subjects from the study when deemed necessary. The circumstances of any discontinuation must be documented in detail in the subject file and final report. If possible, the evaluations planned for the end of study will be carried out at the time when the subject is withdrawn from the study. A subject leaving the study prematurely will be replaced by another if study attrition exceeds the planned 20%. It is understood by all concerned that an excessive rate of withdrawals can render the study un-interpretable; therefore, unnecessary withdrawal of subjects will be avoided.

Criteria for removal of subjects from the study by qualified investigator will include:

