### 9.3 Populations for Analyses

The intention-to-treat analysis method will be followed for trial outcomes. In the case of missing data due to participants that withdrew from the trial or missed visits, data from the previous visit will be used for the missing value (Last Observation Carried Forward, or LOCF).

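### Section 6.4 censors participants outside 80–120% compliance without defining the term or the compliance period, and section 9.3 does not say how that rule fits intention-to-treat with LOCF

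*Combined protocol and SAP*

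**What the plan says.** All references are to the combined protocol and SAP.

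- **6.4** computes compliance as dosage units taken over units expected, then states: "Subjects found to have a compliance of <80% or >120% will be censored from the study". It gives no definition of *censored* and no period.
- **6.2.1** has unused tablets collected at day 28 and day 56. It lists no count at day 84.
- **9.3** states: "The intention-to-treat analysis method will be followed for trial outcomes". Scores missing through withdrawal or missed visits are filled with the previous visit's value. No per-protocol or other compliance-based set is defined.
- **7.1** says that stopping product does not end participation, and that "remaining study procedures should be completed as indicated by the study protocol".
- **7.2.2**, on removal by the investigator, says: "If possible, the evaluations planned for the end of study will be carried out at the time when the subject is withdrawn".
- **7.2.2.2** counts failure to take product as directed as non-compliance. It uses data gathered up to withdrawal or removal. For participants who decide to end participation, it limits further contact to product recovery and an attempt at safety tests, anthropometrics and vitals.
- **9.4.2** plans linear and generalized mixed models, with Aligned Rank Transformation ANOVA as the fallback.

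None of 7.1, 7.2.2, 7.2.2.2 or 9.3 mentions the 80–120% band.

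**The concern.** Compliance is measured after randomisation and may be affected by treatment. A rule that acts on it can therefore change who is compared, or which of their scores are observed.

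If *censored* means dropped from the analysis, the primary comparison is selected on a post-randomisation measure, the balance given by randomisation is no longer guaranteed, and 6.4 contradicts 9.3. If it means removed from the study, the intention-to-treat label survives, but a removal at day 28 or day 56 turns the later scores into carried-forward ones. The 12-week contrast of section 9.1 then mixes day-84 scores with earlier ones. This reading must also be squared with 7.1, under which someone who stops product stays in follow-up.

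The missing period is a separate gap, because it decides both who is caught and whether the rule can act before day 84.

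**Working it through.** **Inputs from the documents.** Two tablets a day for 84 days (6.1.2), so 56 expected per 28 days and 168 in total; 62 per arm (4.1); effect 0.8 SD, alpha 0.01, power 0.90 (9.2); two-sided 0.05 for analysis (9.4.2). The plan's sample size reproduces: a two-sided two-sample t-test gives n = 48.19, so 49 per group. With the 20% attrition of 7.2.2, 49/0.80 = 61.25, so 62. The sample size is not in question here.

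**Step 1: the period.**
- Six missed days in one 28-day period: (56 − 12)/56 = 44/56 = 78.6%, below the limit. Five missed days: 46/56 = 82.1%.
- The same six-day participant, fully compliant otherwise: (44 + 56 + 56)/168 = 156/168 = 92.9%, inside the band.
- Over 84 days it takes 17 missed days: 134/168 = 79.8%. Sixteen gives 136/168 = 81.0%.

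**Step 2: how many the rule could reach.** The documents give no non-compliance rate. Assumed: 5% or 10% of days missed on average, varying between people (beta-binomial, ICC 0.05 to 0.10).

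| Mean days missed | Below 80% in period 1 or 2 (known by day 28 or 56) | Below 80% over 84 days |
|---|---|---|
| 5% | 6%–9% | 2%–5% |
| 10% | 21%–23% | 11%–15% |

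The third 28-day period is left out of the middle column because a shortfall there is known only at about day 84. The right-hand column would need a final tablet count, which 6.2.1 does not list.

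**Step 3: removal at day 28 with LOCF.** Let c be the fraction censored in each arm and g the share of the day-84 effect already present at day 28. Assume that censored participants would otherwise have shown the same day-84 effect. Then

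LOCF contrast = 0.80 × [1 − c(1 − g)].

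| Assumed onset | g | c = 10% | c = 20% |
|---|---|---|---|
| Linear to day 84 | 1/3 | 0.75 | 0.69 |
| Linear, plateau at day 56 | 1/2 | 0.76 | 0.72 |
| Exponential, 14-day half-time | 0.75/0.984 = 0.76 | 0.78 | 0.76 |
| Plateau by day 28 | 1 | 0.80 | 0.80 |

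For removal at day 56 with linear onset, 0.80 × (1 − c/3) gives 0.77 and 0.75. If compliance is judged only at day 84, an attended final score is already observed and nothing changes. In the least favourable cell (0.693 SD, 62 per arm, two-sided t-test), power is about 97% at alpha 0.05.

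With no true effect, equal rates give no false difference. With an assumed 15% versus 5% removed at day 28 and a shared linear improvement of 0.5 SD, the false difference is 0.10 × 2/3 × 0.5 = 0.03 SD.

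**Step 4: exclusion from analysis, no true effect.** Assume 20% versus 10% excluded, with non-compliers δ = 0.3 to 0.8 SD worse than compliers.
- False difference = (0.20 − 0.10) × δ = 0.03 to 0.08 SD.
- SE = √(1/49.6 + 1/55.8) = 0.195 SD, where 49.6 and 55.8 are 80% and 90% of 62.
- Rejection rate P(|Z + bias/SE| > 1.96) = 5.3% to 6.9% at nominal 5%.
- Equal exclusion rates with the same δ give no false difference.

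**The case against.** The strongest reply is that the plan already contains a coherent route. Section 6.4 speaks of the study, not the analysis. Section 7.2.2.2 lists not taking product as directed as non-compliance and keeps the data of anyone removed. Section 9.3 then applies intention-to-treat with LOCF. On that route nobody leaves the primary comparison.

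Much of this stands. A reader might infer from 6.4 that non-compliers are to be deleted from the primary analysis. The documents do not say so, and removal with data kept fits the rest of the text better. But 7.2.2.2 gives no threshold and never refers to 6.4, and nothing in that route supplies the compliance period or the timing, or squares removal with 7.1.

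A reader might also infer a material bias. The documents do not support that either: nothing in them suggests unequal non-compliance between arms, equal rates give no false effect, and the loss under removal disappears if onset is quick. Section 2.1 mentions only anecdotal improvement within days, so linear onset over 84 days is the least favourable of the shapes shown, not an established one.

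Finally, the upper limit looks inconsistent with dispensing: 60 tablets against 56 expected is at most 107.1%, if the first allotment is also 60. A limit that scheduled dispensing cannot reach changes nobody's status, so it is not part of this point.

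It can also be said that LOCF was pre-specified and that replacing it is a preference. That is a reason to keep reporting it. It does not justify filling in scores that the planned mixed models do not need.

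**Conclusion.** The point holds: 6.4 states an operative rule whose meaning, period and timing are undefined, and 9.3 does not say how the primary analysis treats the people it catches. Exclusion would contradict 9.3. Removal, the likelier reading, would produce carried-forward scores if the rule acts at day 28 or day 56.

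The likely size is modest. With a true 0.80 SD and removal at day 28, the LOCF contrast is 0.75–0.80 SD at 10% censored and 0.69–0.80 SD at 20%. Under exclusion with an assumed 20% versus 10% imbalance, the false difference is 0.03–0.08 SD. All of this rests on assumed rates, adherence variation, differences between compliers and non-compliers, and onset shapes. Confidence is high in the gap in the text, not in any particular bias. It should be fixed because the choice of reading would otherwise be open when the data are analysed.

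**What to change.** - **9.3:** state that the primary analysis includes all randomised participants by assigned arm, with every observed score, whatever their compliance, including any who are replaced under 7.2.2.
- **6.4 and 9.3:** state that, for analysis, the 80–120% band only defines a labelled supportive per-protocol set, and give the period over which compliance is computed. If that is 84 days, a final tablet count is needed.
- **9.4.2:** fit the planned mixed models to observed visits. Keep the stated LOCF analysis as a labelled sensitivity analysis, and for the Aligned Rank Transformation ANOVA fallback if that needs complete data.
- **Transparency:** report the LOCF result alongside, date the change, and state how the 6.4 rule was actually applied. Version 4.0 is dated February 2022 and section 5.5 planned enrolment to end in March 2019, so the change may come after the data are known.
- **Reconcile 6.4, 7.1, 7.2.2 and 7.2.2.2** on whether non-compliant participants stay in follow-up and which efficacy assessments they complete. That choice is the sponsor's.

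The cost is some wording and one extra model run on data already collected. The observed-visit model relies on scores being missing at random, and new wording cannot recover visits already skipped.

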## **7. Study Intervention Discontinuation and Participant Discontinuation / Withdrawal**

### **7.1 Discontinuation of Study Intervention**

Discontinuation from Proglucamune® or placebo does not mean discontinuation from the study, and remaining study procedures should be completed as indicated by the study protocol. If a clinically significant finding is identified (including, but not limited to changes from baseline) after enrollment, the investigator or qualified designee will determine if any change in participant management is needed. Any new clinically relevant finding (harm) will be reported as an adverse event (AE).

The data to be collected at the time of study intervention discontinuation will include the following: laboratory safety tests, anthropometrics, and vitals.

### **7.2 Participant Discontinuation/Withdrawal from Study**

The following list of criteria will be used as guidelines concerning the discontinuation (i.e., removal and/or early withdrawal) of subjects from the study:

#### **7.2.1 Personal Reasons**

As stated in the Informed Consent Form, a subject may withdraw from the study for any reason at any time.

#### **7.2.2 Removal by Qualified Investigator**

The Investigator has the discretion to remove subjects from the study when deemed necessary. The circumstances of any discontinuation must be documented in detail in the subject file and final report. If possible, the evaluations planned for the end of study will be carried out at the time when the subject is withdrawn from the study. A subject leaving the study prematurely will be replaced by another if study attrition exceeds the planned 20%. It is understood by all concerned that an excessive rate of withdrawals can render the study un-interpretable; therefore, unnecessary withdrawal of subjects will be avoided.

Criteria for removal of subjects from the study by qualified investigator will include:

### **7.2.2.1 Clinical Reasons**

A subject may be withdrawn from the study if, in the opinion of the Qualified Investigator, it is not in the subject's best interest to continue. Any subject who experiences a serious adverse event (SAE) will be withdrawn from the trial. A participant will also be withdrawn due to adverse events causing clinically significant illness or the need for prohibited medication(s) during the trial. Any female subject who becomes pregnant during the course of the trial will be withdrawn.

### **7.2.2.2 Protocol Violation**

Any subject found to have entered this study in violation of the protocol will be discontinued from the study at the discretion of the Qualified Investigator. This will include any subject found to have been inappropriately enrolled (did not meet eligibility criteria). Subject non-compliance includes not showing up for study visits, not taking the investigational product as directed, or refusing to undergo study visit procedures. Subjects who are found to be taking prohibited medications or supplements without the knowledge of the Qualified Investigator will also be withdrawn. Any major protocol deviations (i.e., those that increase the risk to subjects and/or compromise the integrity of the study or its results) will result in subject discontinuation.

In case of an early withdrawal or discontinuation, no follow-up other than recovery of the investigational product and an attempt to perform laboratory safety tests, anthropometrics, and vitals will be done for the subjects who decide to end their participation, except if the withdrawal was due to medical reasons related to the study. In this case, subjects will be followed-up until recovery. If a subject withdraws or is removed from the study, information collected up until the point of withdrawal will be used unless the subject requests otherwise. The circumstances of any discontinuation will be documented in detail. A subject leaving the study prematurely will be replaced by another if study attrition exceeds the planned 20%. Subjects will be compensated for the part of the study that has been performed.

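### Sections 7.1, 7.2.2 and 7.2.2.2 overlap and conflict on outcome collection after stopping, leaving removed participants and voluntary leavers without a day-84 PQD score

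*Combined protocol and SAP*

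**What the plan says.** All references are to the combined protocol and SAP.

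- **Section 7.1** separates stopping tablets from leaving the study: "remaining study procedures should be completed as indicated by the study protocol". For the moment of stopping it adds: "The data to be collected at the time of study intervention discontinuation will include the following: laboratory safety tests, anthropometrics, and vitals".
- **Section 7.2.2**, on removal by the Qualified Investigator: "If possible, the evaluations planned for the end of study will be carried out at the time when the subject is withdrawn from the study".
- **Section 7.2.2.2**, under the heading on protocol violation: "no follow-up other than recovery of the investigational product and an attempt to perform laboratory safety tests, anthropometrics, and vitals will be done". The paragraph opens by covering early withdrawal or discontinuation in general. The sentence then narrows to subjects who themselves choose to stop taking part. It excepts withdrawals for study-related medical reasons, which are followed to recovery with no efficacy assessment named. Data collected before withdrawal are kept unless the subject objects.

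Other sections turn several reasons for stopping tablets into removal or censoring. Section 7.2.2.1 states: "Any subject who experiences a serious adverse event (SAE) will be withdrawn from the trial". It adds withdrawal for clinically significant illness caused by an adverse event and for need of a prohibited medication. Section 7.2.2.2 says: "Subject non-compliance includes not showing up for study visits, not taking the investigational product as directed". Section 6.4 censors participants whose tablet compliance is below 80% or above 120%.

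On analysis, Section 9.1 sets the primary endpoint as change in Protective Qi after 12 weeks. Section 9.3 states: "The intention-to-treat analysis method will be followed for trial outcomes". It fills missing values by last observation carried forward (LOCF).

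**The concern.** An intention-to-treat comparison at week 12 needs a week-12 outcome on as many randomised participants as can reasonably be measured, including those who stopped treatment. Section 7.1 is written in that spirit. The removal sections work against it, because a participant who stops tablets for illness, non-compliance or a prohibited drug may be moved out of the study, and scoring then ends or is reduced to one exit visit.

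Two things are at stake. First, sites can apply different rules to the same participant, so who has a week-12 score depends partly on which paragraph was read. Second, for those removed, the analysed week-12 value is an earlier measurement. If removal is related to how the participant is doing, or differs between arms, the comparison can be biased, and an observation never taken cannot be recovered at analysis.

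**Working it through.** **1. The rules side by side.** Section 8.1 uses the PQD score from every visit.

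| Situation | Provision | PQD at exit | PQD at day 84 |
|---|---|---|---|
| Stops tablets, stays in study | 7.1 | Not listed at the moment of stopping | Yes, through the remaining visits |
| Removed by investigator | 7.2.2 | If possible | None provided |
| Removed by investigator, if the 7.2.2.2 paragraph is applied | 7.2.2.2 | None named | None |
| Withdrawn for study-related medical reasons | 7.2.2.2 exception | None named | None named |
| Chooses to leave | 7.2.2.2 | None named | None |

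**2. One participant under each rule.** The visits at days 28, 42, 56 and 84 are Visits 3, 4, 5 and 7, and Appendices 1 and 3 give two-weekly appointments. Visit 2 therefore falls at about day 14 and Visit 6 at about day 70. Take someone who stops tablets at day 20.
- Section 7.1: five further scores (days 28, 42, 56, 70 and 84).
- Section 7.2.2: at best one score, near day 20.
- Section 7.2.2.2: nothing after day 14, and LOCF carries that value 84 − 14 = 70 days.

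**3. The plan's sample size.** Inputs from Section 9.2: d = 0.8, alpha 0.01, power 0.90. A two-sided two-sample t-test gives 48.19, rounded up to the stated 49 per group. Allowing for the 20% attrition in Section 7.2.2: 49/(1 − 0.20) = 61.25, rounded up to 62, the arm size in Section 4.1.

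**4. How many could be affected.** 62 × 0.20 = 12.4 per arm, and 124 × 0.20 = 24.8 overall (26 of the 130 in the Synopsis). This is an upper illustration. It puts all planned attrition on a path with no week-12 score, and the documents give no split by type of leaver.

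**5. Power.** With completers only, 62 × 0.80 = 49.6 per group gives power of 0.91 at alpha 0.01. Under LOCF, let f be the share of the treatment effect already present in a leaver's carried value. This is an assumption, with range 0 to 1 and SD unchanged. Then the effective d = 0.8 × [1 − 0.20 × (1 − f)].

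| f | Effective d | Power, alpha 0.01 | Power, alpha 0.05 |
|---|---|---|---|
| 1 | 0.80 | 0.965 | 0.993 |
| 0.5 | 0.72 | 0.916 | 0.978 |
| 0 | 0.64 | 0.826 | 0.942 |

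Both alphas are shown because Section 9.2 sizes at 0.01 and Section 9.4.2 tests at 0.05.

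**6. Bias.** Suppose leavers in both arms would have changed by the same m SD between last observation and week 12, with leaving rates qT and qC. The LOCF error in the arm difference then has size |qT − qC| × |m|. With 20% in both arms it is 0. With 25% against 15% and m = 0.25 it is 0.025 SD. With 30% against 10% and m = 0.5 it is 0.10 SD. These rates and drifts are all assumed. The documents give neither the sign of m nor the arm that loses more, so no direction follows.

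**The case against.** The strongest reply is that the three sections address three groups: those who stop product, those the investigator removes, and those who choose to go. Part of this stands. Under Section 7.1 the short list at discontinuation does no harm in itself, because PQD scoring continues at later visits. The no-follow-up sentence, read literally, concerns people who decide to leave, and someone who refuses further contact cannot be measured under any rule. What does not stand is that the boundaries are clear. The 7.2.2.2 paragraph sits under investigator removal and opens in general terms, and not taking tablets as directed counts there as non-compliance while Section 7.1 keeps people who stop tablets in the study.

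It is also fair that data up to withdrawal are kept, that Section 7.2.2 seeks an exit evaluation, and that the arm size allows for 20% attrition. An exit score is still not a week-12 score, and inflating the sample protects power only. Section 4.4 refers to a Schedule of Activities in Section 1.3 that is not in the text available for this review, so an early-termination visit listed there could not be checked.

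Three stronger readings are tempting, and the documents do not support them.

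- *The no-follow-up rule governs most leavers.* No breakdown of leavers is given, and the rule's own wording limits its scope.
- *Almost nobody can follow the 7.1 path, since even a missed visit means removal.* A missed visit is listed as non-compliance but is not said to lead to removal. Section 9.3 expects participants with missed visits in the analysis. Section 7.2.2 says needless withdrawals are to be avoided.
- *Removal for a cold hides a worsening and flatters the score.* Cold frequency carries 25% in Table 1, so each cold is worth 1 × 0.25 = 0.25 points and the item at most 3 × 0.25 = 0.75. That is item arithmetic and does not estimate bias. Colds are not stated to be a ground for removal: a current cold is a stratification factor in Section 6.3, and Appendices 1 and 3 anticipate colds during the trial. An exit evaluation could capture the illness. The item looks back two months, so a cold before about day 84 − 60 = 24 would not count at day 84. An early carried score can also retain colds from before baseline, which pulls the other way.

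**Conclusion.** The concern holds as a conflict between sections with a definite consequence. Participants removed by the investigator have no day-84 PQD score under any provision in the text and at best one score at exit; voluntary leavers have none after leaving. Their week-12 value in the intention-to-treat analysis is an earlier value carried forward. Participants who only stop tablets under Section 7.1 are not affected.

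At most about 12 of 62 per arm would be involved, if all planned attrition fell on these paths. On that assumption power at alpha 0.01 stays between 0.83 and 0.97, depending on the assumed share of effect in the carried value, so lost power is not the main issue. The exposure is to bias from loss that may relate to outcome or differ by arm. Its size and direction cannot be derived from the documents, and a reader should not infer that it favours the product.

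**What to change.** Reconcile Sections 7.1, 7.2.2 and 7.2.2.2 into one data-collection rule, stating for each type of leaver what is assessed at exit and at day 84.

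- Participants who stop tablets, or are removed by the investigator, are asked to attend the remaining scheduled visits to day 84 for PQD, traditional diagnosis, Generic Qi Deficiency (GQD), saliva IgA and the questionnaires, unless they withdraw consent to data collection.
- Anyone ending participation is offered these efficacy assessments once at exit, and they are added to the lists in 7.1 and 7.2.2.2.
- Section 6.4 is aligned, so that poor tablet compliance does not by itself end outcome collection.

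The cost is amendment wording and a few additional visits of an existing type, with no new instruments or staff. Little will be recovered from people who withdraw consent.

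Section 5.5 dates enrolment from December 2018 to March 2019 and this version is dated February 2022. If follow-up is already complete, report instead the number with an observed week-12 score by arm and by reason for leaving.

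When tablets are stopped, or a participant is withdrawn from treatment, is a clinical matter on which no rule is proposed here; the sections need only be made consistent.
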